StrataGraft skin tissue is applied once to no more than 3 noncontiguous burn sites, totaling a maximum study treatment area of no more than approximately 2000 cm², and using no more than 20 tissues.

Duration of Treatment:

Subject evaluated for 24 weeks after the StrataGraft skin tissue placement

Reference Therapy, Dosage and Mode of Administration:

None

Statistical Methods:

For all safety assessments, the data will be summarized with descriptive statistics.

For all other outcomes, the data will be summarized with descriptive statistics and some of these with 95% confidence intervals. The Kaplan-Meier estimate will be computed to determine the median time to confirmed wound closure without autograft placement (verified with confirmation assessment). No hypothesis testing will be conducted.

Protocol MNK01053115
Amendment 1

StrataGraft

SUMMARY OF CHANGES FOR AMENDMENTS

Amendment 1 was primarily initiated due to the need for provisions for publicly stated emergencies. Additionally, DSMB safety monitoring has been replaced with monitoring by a Sponsor Safety Committee, safety laboratory assessments added, and clarification added for wound assessments, for collection of photographs, for collection of data for prescription medications plus other minor changes and administrative changes. [Appendix 1](#) provides all changes in detail.

Approved

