12. SAFETY ASSESSMENT

Safety will be monitored from the time of subject signing consent to participate in the study and includes: TEAEs, treatment-emergent SAEs, local wound infections, systemic infections, vital signs, and deaths throughout the study duration. In addition to the collection of common clinical study safety data, blood samples (blood plasma and leucocytes) will be collected to comply with the archival xenotransplantation FDA requirements.

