12.2.4. Refactoring and Delayed Wound Healing

In the event that a StrataGraft-treated area needs to be regrafted with either an autograft or a xenograft after prior treatment with StrataGraft skin tissue, the event would not be marked as an AE, but rather as a failure to close. In the event that there is an accompanying wound degradation event occurring simultaneously such as infection that results in delayed wound healing, the delayed wound healing secondary to the ongoing infection can be listed as an AE or SAE as applicable. If that infective process eventually warrants regrafting, the regrafting should still be marked as a failure to close and not an AE.

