13.3.2. Other Pre-specified Endpoint Analyses

For this study, confirmed wound closure is defined as meeting wound determinations at 2 visits:

1. First, a visit at which the clinician determined complete (100%) re-epithelialization without drainage
2. Second, an assessment at a subsequent visit that is at least 2 weeks later than the first visit and wound closure was confirmed (ie, determined again) to be completely closed

Durable wound closure is achieved when a wound is observed as remaining closed at least 3 months after complete wound closure.

The clinician may determine confirmed wound closure and durable closure either by directly observing the wound or by assessing appropriate photo-documentation that will be provided electronically by the subject weekly for the first 12 weeks and then provided every other week through to Week 24. The following endpoints will be analyzed with descriptive statistics with 95% confidence intervals:

- Proportion of subjects with confirmed wound closure without autograft placement (ie, complete re-epithelialization without drainage and subsequently verified with confirmation assessment) on or before Week 12 and supported by photo-documentation
- Proportion of subjects with confirmed wound closure without autograft (verified with confirmation assessment) at each visit and supported by photo-documentation
- Proportion of subjects without autografting who maintain durable wound closure by Week 24
- Time to confirmed wound closure without autografting (verified with confirmation assessment)
- Treatment site skin quality data: The total observed POSAS by clinician and by subject. Per site descriptive statistics will be presented separately for clinician and subject values for each of the individual POSAS items and the total POSAS score, represented as the mean score across all treatment sites and supported by photo-documentation
- Number (%) of subjects with wound infection-related events

The time to first confirmed wound closure (verified with confirmation assessment) will be analyzed by the Kaplan-Meier estimation method. The period for this analysis is calculated as (the date of having the first event – the date of Day 1 + 1). Subjects not having any event during the study will have their time censored at the last available date in the study. Kaplan-Meier estimates by StrataGraft treatment area with confirmed wound closure will be presented for the following categories: $\leq 500 \text{ cm}^2$, $> 500 \text{ cm}^2$.

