3.8.2 Other Endpoint Analyses

The other endpoints of this study are:

- **Proportion of subjects with confirmed complete wound closure of all treatment sites without autograft (i.e., complete re-epithelialization without drainage and subsequently verified with confirmation assessment) on or before Week 12, supported by photodocumentation.**

Complete wound closure is defined as 100% skin re-epithelialization in absence of drainage and without autograft placement. Successful wound closure in this study requires that complete wound closure on or before Week 12 is achieved without autograft placement and is confirmed at least 14 days following the initial observation of complete closure.

The investigator will evaluate the confirmation of complete wound closure either by direct clinician observation or by subject-provided photodocumentation.

The proportion of subject with all confirmed complete treatment site closure(s) including two-sided 95% confidence intervals based on the normal approximation to the binomial will be calculated and presented.

- **Proportion of subjects with confirmed complete wound closure of all treatment sites without autograft (verified with confirmation assessment) at each visit, supported by photodocumentation.**

The planned visits are Week 1, Week 2, Week 4, Week 8, Week 12, and Week 24. However, the subjects may show up at any visit, and number and percentage will be summarized. For each visit, the denominator of the proportion of subjects is based on the total number of subjects who provided data for the visit.

- **Proportion of subjects maintaining durable wound closure by Week 24.**

Durable wound closure by Week 24 is achieved when a subject with confirmed wound closure is observed as remaining closed at least 90 days after complete wound closure through Week 24. Two summaries will be performed: 1. Denominator is mITT population 2. The denominator will be based on subjects with confirmed wound closure of all treatment sites without autograft by Week 12. The number, percentage and two-sided 95% confidence intervals based on the normal approximation to the binomial will be calculated and presented.

- **Proportion of treatment sites with confirmed complete wound closure without autograft (i.e., complete re-epithelialization without drainage and subsequently verified with confirmation assessment) on or before Week 12 and supported by photodocumentation.**

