The treatment sites will be analyzed regardless of subject. Treatment site with confirmed wound closure requires treatment site complete closure on or before Week 12 is achieved without autograft placement and is confirmed at least 14 days following the initial observation of complete closure.

The investigator will evaluate the confirmation of complete treatment site closure either by direct clinician observation or by subject-provided photodocumentation.

The proportion of confirmed complete treatment site closure including two-sided 95% confidence intervals based on the normal approximation to the binomial will be calculated and presented.

- **Proportion of treatment sites maintaining durable wound closure by Week 24.**

The treatment sites will be analyzed regardless of subject.

Durable wound closure by Week 24 is achieved when a confirmed wound is observed as remaining closed at least 90 days after a confirmed complete wound closure through Week 24. Two summaries will be performed: 1. Denominator is all treatment sites 2. The denominator will be based on a confirmed treatment site wound closure by Week 12. The number, percentage and two-sided 95% confidence intervals based on the normal approximation to the binomial will be calculated and presented.

- **Time to first confirmed complete wound closure of all treatment sites in a subject without autograft (verified with confirmation assessment at least 14 days later).**

The event for Kaplan-Meier method will be the first occurrence of all confirmed complete wound closure without autograft in a subject (first observation of complete closure verified with a second observation of complete closure at least 14 days later). The time to first confirmed wound closure will be analyzed by the Kaplan-Meier estimation method. The period for this analysis is calculated as (the date of having the first confirmed event – the date of Day 1 + 1). Subjects not having any confirmed complete closure event during the study will have their time censored at the last available date in the study. Kaplan-Meier estimates by StrataGraft treatment area with confirmed wound closure will be presented for the following categories: $\leq 500 \text{ cm}^2$, $> 500 \text{ cm}^2$.

The Kaplan-Meier estimate will be computed to determine the median time to confirmed complete wound closure without autograft placement.

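### The Kaplan-Meier rule censors subjects who can no longer close without autograft, so the closure curves are biased upward if such subjects leave before Week 24

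*SAP*

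**What the plan says.** - **Estimator.** SAP 3.8.2: "The time to first confirmed wound closure will be analyzed by the Kaplan-Meier estimation method". SAP 3.1 and 3.8.2 take the median from it, with a Brookmeyer-Crowley interval. Separate estimates are planned for treated areas up to and above 500 cm².
- **Event.** "The event for Kaplan-Meier method will be the first occurrence of all confirmed complete wound closure without autograft in a subject". The same section states: "Complete wound closure is defined as 100% skin re-epithelialization in absence of drainage and without autograft placement".
- **Censoring.** SAP 3.8.2: "Subjects not having any confirmed complete closure event during the study will have their time censored at the last available date in the study". Protocol 13.3.2: "Subjects not having any event during the study will have their time censored at the last available date in the study".
- **Regrafting.** If a treated site is regrafted with autograft or xenograft, Protocol 12.2.4 says "the event would not be marked as an AE, but rather as a failure to close".
- **Deaths.** Protocol 12 lists the safety data collected as "TEAEs, treatment-emergent SAEs, local wound infections, systemic infections, vital signs, and deaths throughout the study duration". Neither document says how a death before closure enters the time-to-closure analysis.
- **Second curve.** SAP 3.8.2 adds a Kaplan-Meier analysis of closure without any grafting (autograft, allograft, xenograft, other skin substitute). It gives no separate censoring rule.
- **Follow-up.** Protocol synopsis: "Subject evaluated for 24 weeks after the StrataGraft skin tissue placement". Regrafting is not a withdrawal criterion (Protocol 7.3), and all subjects are to be followed to completion (Protocol 6.1.4).

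Neither document mentions competing events, cumulative incidence, or a rule that keeps known failures at risk to Week 24.

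**The concern.** Kaplan-Meier treats a censored subject as having, from that day on, the same chance of closing as those still under observation. For a subject with an autografted treatment site, or one who has died, that chance is zero by the definition of the event. Removing such a subject from the risk set before Week 24 in effect shares out closures to someone who cannot close, and the curve rises.

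At stake is the probability of closure without autograft that a reader takes from the plotted curves. The same report gives the Week 12 proportion on the mITT population (SAP 3.2 and 3.8.2), which can count these subjects as non-closers. The two figures can then differ with no stated reason. If autograft or death is more common in one area category than in the other, the two area curves are distorted unequally. SAP 1 allows for use of the results in regulatory submissions and manuscripts.

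**Working it through.** The plan states no expected closure rate, median, autograft rate, death rate or dropout rate, so there is no figure to reproduce. What follows shows how the rule behaves under assumed rates.

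**Inputs.** N = 100 (approximate enrolment, SAP 2.3). Nominal Week 24 is day 24 × 7 + 1 = 169, and Week 12 is day 12 × 7 + 1 = 85, using the SAP's day count. Assumed: K known failures (autografted or dead); a share s of them leaves early; C subjects close by day 85; everyone else is followed to day 169.

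**Formula.** With no other early censoring, the actual proportion closed by Week 12 is C/N. If sK failures leave after g closures have occurred, the SAP rule gives

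1 − KM = 1 − [(N − g)/N] × [(N − C − sK)/(N − g − sK)].

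With g = 0 (all leave before the first closure) this becomes C/(N − sK).

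**Worked case.** K = 10, and 85% of the other 90 close by Week 12, rounded to C = 76, at days 15, 29, 57 and 85 in numbers 8, 27, 27 and 14.

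- All ten stay to Week 24: 76/100 = 76.0%, equal to the actual proportion. No bias.
- Five leave on day 10: 76/95 = 80.0%. All ten: 76/90 = 84.4%.
- Five leave on day 29, after g = 35 closures: 1 − 0.65 × 19/60 = 79.4%. All ten: 1 − 0.65 × 14/55 = 83.5%.

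**Range.** Leaving on day 10, 29 or 43, and closures split 10/35/35/20 or 5/20/35/40 over the four days. Closure by Week 12:

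| Closure among the others | K | Actual, and SAP rule if all stay | SAP rule if all K leave early |
|---|---|---|---|
| 85% | 5 | 81% | 84.8-85.3% |
| 85% | 10 | 76% | 83.5-84.4% |
| 85% | 20 | 68% | 83.1-85.0% |
| 60% | 5 | 57% | 59.2-60.0% |
| 60% | 10 | 54% | 58.5-60.0% |
| 60% | 20 | 48% | 57.0-60.0% |

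All failures leaving early is the extreme. The largest gap in the table is 85.0 − 68 = 17 points.

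**Partial loss.** A simulation used lognormal closure times (median 40 days, log-scale SD about 0.62), weekly assessment, and leavers exiting between Days 14 and 79. With 30-60% of the failures leaving early, the upward bias at Day 85 was:

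- 5% failures: about 1 to 2 points;
- 10% failures: about 2 to 4 points;
- 20% failures: up to 6.6 points.

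At Day 169 with 10% failures, Kaplan-Meier gave about 92-94% against 89% actual. With no early loss the bias was zero throughout. Only autografted subjects were modelled as failures there. A death before closure acts in the same way, with s = 1.

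**Median.** It did not change in that simulation. In the constructed data it moved in a few settings only: from not reached to day 85 (K = 20, 60% closure among the others), and from day 85 to day 57 (85% closure, the slower split, all failures leaving on day 10).

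**The case against.** The case against giving this much weight is substantial.

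- The only named summary of the curve is the median, which seldom moves. Neither document says that Day 85 or Day 169 probabilities will be read from the curve. This stands, but the area-specific estimates are still to be presented.
- The closure probability is reported elsewhere: the Week 12 proportion with its interval, plus the regrafting summaries in SAP 3.8.2. This limits the harm. It does not correct the curve, and it is where a disagreement would show.
- A reader might infer that autografted subjects are censored at the autograft, or that they tend to leave because they have no reason to stay. The documents support neither. Censoring is at the last available date, regrafting does not end follow-up, and the primary safety endpoint runs for about 24 weeks. No motive or rate of leaving is given.
- Failures may be few. Protocol 4.3 reports that in the Phase 1b study no subject was autografted before Day 28 and that 27 of 28 per-protocol subjects (96%) were closed at Month 3. Those treated areas were at most 440 cm², against about 2000 cm² allowed here, so the rate may not carry over.
- Exclusion criterion 7 (expected survival under 3 months) makes deaths less likely, but follow-up lasts 24 weeks and deaths remain possible.
- The endpoint is descriptive. At 80% closure and N = 100 the 95% half-width is 1.96 × √(0.8 × 0.2/100) = 7.8 points, larger than the bias in the milder scenarios. Bias in one direction is still worth removing when the remedy is cheap.

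None of this changes the censoring rule or protects the curve against death or loss to follow-up.

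**Conclusion.** The point holds conditionally. The stated rule censors subjects whose event has become impossible, and the curves are biased upward to the extent that such subjects exit before Week 24. It would go too far to say that the curve overstates closure in any event: if every autografted subject completes Week 24 and nobody dies before closure, the rule gives the right answer.

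The size cannot be settled from the documents. The figures of about 1 to 2 points at Week 12 (5% failures, 30-60% leaving early) and 2 to 4 points (10%) rest on assumed rates and an assumed closure-time distribution. They are illustrations, not expected bias. The effect on the median is usually nil. This is a minor improvement to a descriptive endpoint and does not affect the primary safety analysis.

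**What to change.** In SAP 3.8.2:

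1. **First curve.** Treat autograft on a treated site, and death, before confirmed closure as competing events and report cumulative incidence (Aalen-Johansen). Alternatively, keep these subjects at risk as non-closers to the nominal Week 24 day. The second option leaves the planned Kaplan-Meier median and its interval in place.
2. **Second curve.** Do the same for any graft on a treated site (autograft, allograft, xenograft, other skin substitute) and for death.
3. **Area-specific curves.** Apply the same handling to both area categories.
4. **Censoring.** Censor at the last available date only subjects who have had none of these events.
5. **Xenograft.** State whether a xenograft on a treated site counts as failure in the first curve. Protocol 12.2.4 calls it a failure to close, while the SAP event excludes only autograft.
6. **Record.** Note the change in SAP 2.2.4, which now declares no major modification, because the method and the censoring rule also stand in Protocol 13.3.2.

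The cost is a few sentences and standard programming. Grafting procedures and deaths are already collected (Protocol 8.3 and 12), and no visits or subjects are added. The downside is a small departure from the protocol's method and a curve that may be slightly lower.

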3.8.3 Subgroup Analyses

The Proportion of subjects with confirmed complete wound closure without grafting on or before Week 12 and TEAE endpoints will be summarized by the following demographic and baseline characteristics:

- Race (white, non-white)
- Ethnicity (Hispanic, non-Hispanic)
- Age (<65, ≥ 65)
- Sex (Male, Female)
- StrataGraft treatment area ($\leq 500 \text{ cm}^2$, $> 500 \text{ cm}^2$)
- StrataGraft treatment area ($\leq 1000 \text{ cm}^2$, $> 1000 \text{ cm}^2$)
- Overall TBSA of wound burden defined as burns plus donor site area (< Median, \geq Median)
- Burn location (Anterior trunk, Anterior Upper Extremity (includes forearm + upper arm), Anterior Lower Leg, Anterior Thigh, Posterior Trunk, Posterior Upper Extremity (includes forearm + upper arm), Posterior Lower Leg, Posterior Thigh)

To further evaluate the burn location effect, Percent of Re-epithelialization without Grafting at each Visit, Proportion of subjects maintaining durable wound closure and POSAS by clinical visit in person by burn location will be summarized.

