6.3. Treatment Assignment

Subjects who meet all inclusion criteria will receive StrataGraft skin tissue treatment. Subjects are considered enrolled into the study once they have StrataGraft skin tissue treatment applied to a burn site. Subjects will receive 1 application of StrataGraft skin tissue(s) to no more than 3 burn sites with no more than 20 StrataGraft skin tissues applied to the burn sites and a total study treatment area of no more than approximately 2000 cm².

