3.7 Treatment and Exposure

The number of subjects with 1, 2, and 3 burn sites, and numbers of StrataGraft constructs applied (per site and total per subject) will be summarized.

The observation duration from Day 1 (application of StrataGraft) to end of study will be summarized.

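### The burn-location subgroup tabulates subject-level closure by an attribute of the individual site, so a location's closure rate can depend on sites elsewhere in the same subject

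*SAP*

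**What the plan says.** SAP 3.8.3 names the endpoints for the subgroup tables: "The Proportion of subjects with confirmed complete wound closure without grafting on or before Week 12 and TEAE endpoints will be summarized" by a list of demographic and baseline factors. Seven entries describe the subject (race, ethnicity, age, sex, treated area at two cut-points, wound burden). The eighth is anatomical: "Burn location (Anterior trunk, Anterior Upper Extremity (includes forearm + upper arm), Anterior Lower Leg, Anterior Thigh, Posterior Trunk, Posterior Upper Extremity", continuing to eight body areas. There is no category for several locations and no rule for assigning a subject treated in more than one.

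A second sentence adds location summaries: "To further evaluate the burn location effect, Percent of Re-epithelialization without Grafting at each Visit, Proportion of subjects maintaining durable wound closure", and POSAS from in-person visits.

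The subject-level Week 12 endpoint is set out in SAP 3.8.2: "Proportion of subjects with confirmed complete wound closure of all treatment sites without autograft". The same section also defines a site-level endpoint, "Proportion of treatment sites with confirmed complete wound closure without autograft", and a site-level durable-closure endpoint. Neither is tied to burn location.

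Subjects can have several sites. Protocol 6.3 states: "Subjects will receive 1 application of StrataGraft skin tissue(s) to no more than 3 burn sites". Protocol 6.1 describes the areas as noncontiguous. SAP 3.7 plans to report "The number of subjects with 1, 2, and 3 burn sites".

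**The concern.** Age or sex takes one value per subject, so a subject-level outcome can be tabulated against it directly. Burn location takes one value per treated wound. A subject treated on the trunk and the thigh has two locations but only one all-sites result. If the trunk site closes and the thigh site does not, that result is failure, and a trunk row that includes the subject records a failure that did not occur on the trunk.

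Assigning each subject to a single location does not cure this, because the outcome would still depend on the sites elsewhere. Only counting sites, or restricting the rows to single-location subjects, separates one location's result from another's. SAP 3.8.3 provides for neither.

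What is at stake is the reading of the location tables for Week 12 closure and durable closure. A location where the product does well can look worse than it is, and a real difference between locations can look smaller.

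**Working it through.** The documents give no subgroup figure, so there is nothing to reproduce. The check is an illustration.

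**Inputs, all assumed unless a source is given**
- Site closure rate at a well-performing location L: pL = 0.95. At a poorer location O: pO = 0.70.
- m = share of subjects in a row who also have a site at the other location: 0.25, 0.5, 0.75 and the extreme 1.
- Two sites per multi-location subject, each such subject counted in both rows, and equal m in both rows.
- pLO = probability that both sites close. Under independence, 0.95 × 0.70 = 0.665.

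**Formulas**
- Row L = (1 − m)·pL + m·pLO
- Row O = (1 − m)·pO + m·pLO
- Gap = (1 − m)·(pL − pO). pLO cancels, so within-subject correlation does not alter the gap.

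**Results under independence (site-level gap 25 points)**

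| m | Row L | Row O | Gap (points) |
|---|---|---|---|
| 0.25 | 0.75×0.95 + 0.25×0.665 = 87.9% | 0.75×0.70 + 0.25×0.665 = 69.1% | 18.8 |
| 0.5 | 0.5×0.95 + 0.5×0.665 = 80.8% | 0.5×0.70 + 0.5×0.665 = 68.3% | 12.5 |
| 0.75 | 0.25×0.95 + 0.75×0.665 = 73.6% | 0.25×0.70 + 0.75×0.665 = 67.4% | 6.3 |
| 1 | 66.5% | 66.5% | 0 |

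**Correlation.** With strong within-subject correlation (latent correlation 0.9 in a Gaussian copula), pLO rises to 0.700. Row O is then correct at 70%, but row L is still low by m × (0.95 − 0.70), which is 6.3, 12.5 or 18.8 points at m = 0.25, 0.5 or 0.75.

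**Unequal m.** Under independence the gap is 25 − 28.5·mL + 3.5·mO points. With mL = 0.25 and mO = 0.75 it is 25 − 7.1 + 2.6 = 20.5. With the shares reversed it is 25 − 21.4 + 0.9 = 4.5. Shrinkage is therefore a tendency whose size depends on which row holds more multi-location subjects.

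**Three sites.** If the two companion sites each close at 70% independently, row L = 0.95 × [(1 − m) + m × 0.49], which is 82.9%, 70.8% or 58.7% at m = 0.25, 0.5 or 0.75.

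**Similar high rates everywhere.** With pL = pO = p, two sites and independence, each row is low by m·p·(1 − p).
- p = 0.96 (Protocol 4.3 reports 27 of 28 per-protocol subjects closed in the Phase 1b study, used here only as a plausible value): 0.0384·m, or 1.0, 1.9 and 2.9 points at m = 0.25, 0.5 and 0.75.
- p = 0.90: 0.09·m, or 2.3, 4.5 and 6.8 points.

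**Counting example (assumed).** Ten subjects are each treated on thigh and trunk. The thigh closes in 10 and the trunk in 7. Counted by site, the rows show 10/10 and 7/10. Counted by the all-sites result, both show 7/10: three site failures appear as six, and the difference disappears.

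**The case against.** The strongest reply is that the defect is partly inferred. SAP 3.8.3 does not repeat the all-sites condition, and it excludes any grafting where the main endpoint in SAP 3.8.2 excludes autograft. The re-grafting list in SAP 3.8.2 uses proportion-of-subjects wording for results shown both by treatment site and overall. The location rows could therefore mean subjects whose site at that location closed. Table shells and programming specifications are separate documents (SAP 5 and 6) and may settle it.

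This stands as a limit on certainty. It does not remove the point. The all-sites definition is the SAP's stated one for the Week 12 subject endpoint, and where the SAP wants a looser rule in that list it says that one site is enough. Display by site A, B or C does not help, because those labels are not anatomical.

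Several stronger inferences are tempting, and the documents do not support them:
- A reader might infer that a failure is counted in every other location row. SAP 3.8.3 never says that a subject enters each row.
- A reader might infer that an adverse event at the thigh will be counted on the trunk row. The text does not say so, and SAP 3.9.1 already reports TEAEs by site A, B and C, pooled sites, non-study burn, donor site and other.
- A reader might take all the location tables as intended to isolate a location effect. That purpose introduces only the second sentence of SAP 3.8.3.
- A reader might conclude that a failing location would be hidden. Re-epithelialization and POSAS by location are also planned and can be read per site, so such a location could show there.

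Also conceded: the analyses are descriptive with no hypothesis tests (SAP 3.8), and burn location is not among the subgroups in Protocol 13.3.4.

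**Conclusion.** The mismatch of unit is real. A subject-level closure result is tabulated by a site attribute, with no rule for subjects treated at several locations. Followed as written, with the SAP 3.8.2 definition, a location's closure or durability rate can depend on sites elsewhere in the same subject. The tendency is to understate well-performing locations and to narrow differences.

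The size cannot be fixed from the documents, because they give neither m nor site rates by location. With the assumed 95% and 70%, two sites and equal m, a 25-point gap falls to 18.8, 12.5 or 6.3 points. With similar high rates everywhere, the understatement is about 1 to 3 points at 96% and 2 to 7 points at 90%. Subjects treated within one location category cause no cross-location error. It would be wrong to say that the error vanishes only when no subject has several locations: it is also nil where each subject's sites all close or all fail together.

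The effect is confined to interpreting descriptive location tables. The primary endpoint, the overall closure results and the subgroups that are subject characteristics are untouched.

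**What to change.** In SAP 3.8.3, for the burn-location rows only, make the treatment site the unit:
- Report the proportion of treatment sites at each location with confirmed closure by Week 12, under the same no-grafting rule as the other subgroup rows, and the proportion with durable closure. Use the site-level definitions already in SAP 3.8.2.
- If intervals are shown, allow for clustering of sites within subject. The plain normal-approximation interval in SAP 3.1 treats observations as independent.
- State how a single site that spans two of the eight areas is classified.
- For TEAEs by location, add a row of events recorded at the StrataGraft site or sites in that location. Leave the overall TEAE tables, including systemic events and events at other sites, unchanged.
- Keep the subject-level endpoints for age, sex, race, ethnicity, total treated area and wound burden.

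The cost is SAP wording and re-programming of the location tables. The SAP already plans closure and TEAEs by treatment site. SAP 3.3 summarises treatment by location without stating the unit, so the sponsor should confirm that location is recorded against each site label. If it is, no new data are needed.
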